4.6.1.2. Immunogenicity

The immunogenicity data collected in adolescent maternal participants 15 to 17 YOA in this trial will be descriptively summarized by treatment group. In addition, a Bayesian approach will be used for further extrapolation of the immune response. It is assumed that the log transformed immune response (for example neutralizing antibody titers) in adolescent maternal participants follows a normal distribution with the mean μ and SD of σ ; it is further assumed that the mean μ is a random variable and has a normal distribution as a prior. The prior normal distribution for the mean μ will be developed based on data collected in maternal participants above 17 YOA in this trial. With the data observed in adolescent maternal participants 15-17 YOA in this trial, a Bayesian approach will be applied to estimate the posterior distribution of the mean μ and the predictive probability of observing a high immune response (for instance, 6 fold increase) for an adolescent maternal participant 15-17 YOA in the RSV-MAT vaccine group. A high predictive probability of having at least 6-fold increase 1 month post-study intervention from baseline in a pregnant adolescent RSV-MAT vaccine recipient will provide reassurance of immune response for an adolescent maternal participant 15-17 YOA receiving the RSV-MAT vaccine.

4.6.2. Subgroup analyses

Subgroup analyses of the primary endpoints will be made to assess consistency of the intervention effect across the following subgroups:

- Age group (for maternal participants): < 18 vs ≥ 18 years
- Gestational age at birth (for infant participants): ≥ 37 weeks; < 37 weeks (as assessed by the GAIA gestational age definition*)
 - * Additional statistical analyses may also be performed by using the Intergrowth-21st (IG-21) standard definition [Villar, 2014].
- Pre-existing HIV infection status: present vs absent (for maternal participants ≥ 18 YOA only)
- Pre-existing obstetric complications: present vs absent (for maternal participants ≥ 18 YOA only)

Except for maternal age group, if the number of participants is too small (less than 10%) within above mentioned subgroup, then the subgroup categories may be redefined prior to final analysis.

To take a more practical approach, subgroup analysis of safety by age category at study intervention administration (< 18 ; ≥ 18 years) in maternal participants will include summaries of solicited administration site and systemic events, unsolicited AEs, MAEs, SAEs, RSV-associated MA-RTIs, (S)AEs leading to study withdrawal, worsening of pre-existing medical conditions and/or obstetric complications, pregnancy outcomes and pregnancy-related AESIs.

Subgroup analysis of safety by gestational age at birth (≥ 37 weeks; < 37 weeks) in infant participants will include summaries of neonatal AESIs, MAEs, SAEs, (S)AEs leading to study withdrawal, and occurrence of RSV-associated LRTIs, any severity and severe LRTIs, RSV-associated hospitalization.

Subgroup analysis on other safety summaries will be performed if deemed necessary.

Subgroup analysis of immunogenicity by age category at study intervention administration (< 18 ; ≥ 18 years) for maternal participants and by gestational age at birth (≥ 37 weeks; < 37 weeks) for infant participants will include analysis of GMT(C) and GMR calculation at each time point and geometric mean of placental transfer.

Subgroup analysis on other immunogenicity analysis will be performed if deemed necessary.

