2.3. Benefit/Risk assessment (Amended 15 March 2022)

The Sponsor has included provisions in this trial to ensure participant's safety. Safety monitoring has been and will be conducted throughout this study by an unblinded Independent Data Monitoring Committee (IDMC) and by the Sponsor. The study includes the establishment of a surveillance system which may facilitate detection of respiratory tract infections, in particular lower respiratory tract infections (LRTIs) in infants enrolled in the study. Measures to suspend the study should a potential safety issue be identified are described in Section 8.2.3.

Following a recommendation from the IDMC, the Sponsor made the decision to pause the enrollment, randomization and vaccination of participants in our active pregnant women studies, including RSV MAT-012, based on an observation of imbalance of the proportion of preterm births between the vaccine group and the placebo group in the RSV MAT-009 study. This pause was to allow for an evaluation of the available data in RSV MAT-009 to better understand the safety signal observed. Following a review of additional unblinded data from this trial in which a higher proportion of neonatal deaths reported in the treatment group compared to the placebo group was also observed, the Sponsor decided to STOP enrollment and vaccination in these studies.

The safety signals are being investigated and, although at this time a cause has not been determined, the Sponsor stopped active enrollment and further vaccination of participants in the RSV MAT studies enrolling pregnant women on February 25, 2022 as a precautionary measure. The study remains ongoing for safety follow-up. Participants already vaccinated and their infants will continue to be monitored until the end of the study.

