9.4. Statistical analyses

9.4.1. General considerations

The SAP will be finalized before database lock and will include a more technical and detailed description of the statistical analyses to be performed. This section summarizes planned statistical analyses of primary and secondary endpoints.

All statistical analyses are descriptive. Besides the primary analyses, sub-group analyses may be conducted based on age group, gestational age at birth (as assessed by the GAIA gestational age definition)*, pre-existing HIV infection, pre-existing obstetric complications and/or breastfeeding status.

* Additional statistical analyses may also be performed by using the Intergrowth-21st (IG-21) standard definition [Villar, 2014].

The SAP will describe how missing data will be handled during analyses.

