** **Due to the recent safety signal, the study was fully unblinded to ensure the safety monitoring of the participants**

2. STATISTICAL HYPOTHESES

No statistical hypotheses will be tested. All statistical analyses are descriptive.

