	
Number and percentage of maternal participants reporting pregnancy-related AESIs * and worsening of pre-existing medical conditions and/or obstetric complications from Day 1 up to 42 days post-delivery. * These include maternal death, hypertensive disorders of pregnancy (gestational hypertension, pre-eclampsia, pre-eclampsia with severe features including eclampsia), fetal growth restriction, gestational diabetes mellitus, pathways to preterm birth (premature preterm rupture of membranes, preterm labor, provider-initiated preterm birth) and chorioamnionitis.
	
The number and percentage of maternal participants reporting each pregnancy-related AESI and worsening of pre-existing medical conditions and/or obstetric complications from Day 1 up to 42 days post-delivery will be tabulated with its exact 95% CI by group.
 
By participant listings of pregnancy-related AESIs and worsening of pre-existing medical conditions and/or obstetric complications will be prepared.

CONFIDENTIAL

	Primary Safety Endpoints	Statistical Analysis Methods
Infant participants	
Number and percentage of infant participants reporting neonatal / infant AESIs * from birth up to 42 days post-birth.
 
* These include small for gestational age, low birth weight including very low and extremely low birth weight (<2500 g, <1500g, <1000g), congenital anomalies (major external structural defects, internal structural defects, functional defects), neonatal death (in an extremely preterm birth [22<GA<28 weeks], in a preterm live birth [28<GA<37 weeks], or in a term live birth) and preterm birth.
	
The number and percentage of infant participants reporting each neonatal / infant AESI from birth up to 42 days post-birth will be tabulated with its exact 95% CI by group.
 
By participant listings of neonatal / infant AESIs will be prepared.

	
Number and percentage of infant participants reporting SAE, (S)AEs leading to study withdrawal, and MAEs from birth up to 42 days post-birth.
	
The number and percentage of infant participants reporting:
 
 • at least one SAE • at least one (S)AE leading to study withdrawal • at least one MAE 
from Day 1 up to 42 days post-birth with exact 95% CIs will be tabulated by group and by MedDRA preferred term.
 
By participant listings of SAEs, (S)AEs leading to study withdrawal and MAEs will be prepared.

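### SAP 4.6.2 judges consistency of the vaccine effect by gestational age at birth, which is itself a post-dosing outcome, and the exploratory infant antibody model in SAP 4.3.3 cuts it on the wrong side of 37 weeks

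*SAP*

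**What the plan says.** SAP 4.6.2 gives its subgroups a purpose: "Subgroup analyses of the primary endpoints will be made to assess consistency of the intervention effect across the following subgroups". Three factors on the list are fixed before the dose: maternal age group, pre-existing HIV infection and pre-existing obstetric complications. The fourth is not: "Gestational age at birth (for infant participants): ≥ 37 weeks; < 37 weeks". The same section says that the tables by this factor "in infant participants will include summaries of neonatal AESIs, MAEs, SAEs, (S)AEs leading to study withdrawal", and it also splits infant antibody results and placental transfer by it.

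The primary infant events in SAP 4.2.1.1 end with "or in a term live birth) and preterm birth". Protocol Table 39 defines preterm birth as under 37 completed weeks (under 259 days), the same cut as the subgroup. Protocol 2.3 says that enrolment was paused "based on an observation of imbalance of the proportion of preterm births between the vaccine group and the placebo group" in RSV MAT-009.

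Three passages limit the issue. SAP 4.2.1.1 keeps the unsplit table: "The number and percentage of infant participants reporting each neonatal / infant AESI from birth up to 42 days post-birth will be tabulated", by group. SAP 2 says: "No statistical hypotheses will be tested. All statistical analyses are descriptive". Protocol 9.4.1 is permissive: "sub-group analyses may be conducted based on age group, gestational age at birth (as assessed by the GAIA gestational age definition" and other listed factors.

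SAP 4.3.3, an exploratory section, defines the infant-model covariate gagebg1 as above 37 weeks versus 37 weeks or below. SAP 4.2.1.1, 4.3.1.1, 4.6.2 and 6.1.2.1 all use 37 or above versus below 37. The antibody ANCOVAs in SAP 4.2.2.1 and 4.3.2.1 also allow the dosing-to-delivery interval as a covariate when needed.

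**The concern.** A subgroup can speak to consistency of a treatment effect only if treatment could not have changed who is in it. Vaccination could change membership of the term and preterm strata, and that possibility is exactly the signal raised in RSV MAT-009. If vaccine brings some births forward, the preterm stratum on vaccine contains infants who would have been term on placebo, so the two arms no longer hold comparable infants within a stratum. A harm that works through earlier birth then appears as more infants in the preterm column, not as a higher rate within it. A reader told that the table assesses consistency of effect could take an equal or lower preterm rate on vaccine as reassurance.

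The antibody models raise the same issue more mildly. Both gagebg1 and the dosing-to-delivery interval arise after dosing, so adjusting for either changes what the between-group ratio estimates. The gagebg1 boundary is also inconsistent with the preterm definition.

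**Working it through.** The plan gives no figure on this point, so there is none to reproduce. Steps 1, 2 and 6 rest on the documents alone. The rates in steps 3 and 4 and the GA distribution in step 5 are assumptions.

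1. **Timing.** The dose is given at 24 0/7 to 36 0/7 weeks (Protocol 4.1, 4.3). GA at birth is observed afterwards for every infant.

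2. **The endpoint defined by the stratifier.** 37 × 7 = 259 days, so the subgroup cut is the preterm definition. Preterm birth is 100% below 37 weeks and 0% at or above it in both arms. The within-stratum difference is 0 whatever the true effect. With assumed preterm rates of 15% on placebo and 22% on vaccine, the overall difference is 7 points and both stratum differences are 0.

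3. **Other infant endpoints.** Assume an SAE in 60% of preterm and 10% of term infants, and risk x in the extra preterm infants on vaccine.
 - Placebo overall: 0.15 × 0.60 + 0.85 × 0.10 = 0.175.
 - Vaccine overall: 0.15 × 0.60 + 0.07x + 0.78 × 0.10. For x = 0.60, 0.45, 0.30 this is 0.210, 0.1995, 0.189, so the risk ratio (RR) is 1.20, 1.14, 1.08.
 - Vaccine, preterm stratum: (0.09 + 0.07x)/0.22 = 0.600, 0.552, 0.505. Against 0.60 the RR is 1.00, 0.92, 0.84.

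 The stratum RR falls below 1 only if the extra preterm infants are assumed healthier than other preterm infants. With x = 0.60 it is exactly 1.

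4. **How often the two tables would disagree.** Simulated trials, one infant per mother. The quantity is the chance that the preterm column is lower on vaccine, given that the overall rate is higher on vaccine. The no-effect column uses the placebo rates in both arms. At 252:126 the first setting has about 252 × 0.22 = 55 preterm infants against 126 × 0.15 = 19.

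| Preterm, placebo vs vaccine | Preterm SAE risk; x | Size | With effect | No effect | Excess, points |
|---|---|---|---|---|---|
| 15% vs 22% | 60%; 60/45/30% | 252:126 | 42/55/66% | 33% | 9.6/22.0/33.5 |
| 15% vs 22% | 60%; 60/45/30% | 126:63 | 39/47/55% | 32% | 7/15/23 |
| 10% vs 13% | 40%; 40/30/20% | 252:126 | 36/41/45% | 33% | 2.5/7/12 |
| 10% vs 13% | 40%; 40/30/20% | 126:63 | 34/37/40% | 32% | 2/5/8 |

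 About a third of such disagreements would occur with no vaccine effect at all. Only the excess belongs to the stratification. Enrolment stopped early and the documents do not give the size reached, hence the half-size rows.

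5. **The gagebg1 cut.** The Protocol glossary records GA as completed weeks plus days, so 37 0/7 (day 259) is a term birth, but the SAP 4.3.3 cut groups it with preterm births. If GA enters the model in whole completed weeks, days 259 to 265 (37 0/7 to 37 6/7) move as well. The SAP does not say which coding applies. Under an assumed normal GA distribution (mean 266 to 276 days, SD 10 to 12), term births would make up 9 to 19% of the lower category with exact coding, or 44 to 72% with whole weeks.

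6. **Antibody models and analysis set.** SAP 4.3.3 treats gagebg1 and the interval as carrying similar information, so swapping one for the other keeps a post-dosing covariate. The infant per-protocol set (SAP Table 4; code 3100 in Table 8) drops births less than 4 weeks after dosing. Removing the covariates on that set therefore still leaves selection on a post-dosing event.

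**The case against.** The strongest reply is that little depends on one lead-in sentence. It covers four subgroups, and SAP 4.6.2 then narrows the infant work to summaries. No interaction test is planned, every analysis is descriptive, the overall column stays, and the protocol itself names GA at birth as a possible subgroup. The preterm signal is also read elsewhere without this split: SAP 4.3.1.2.4 counts preterm births per pregnancy, and pathways to preterm birth is a primary maternal endpoint tabulated by group.

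All of that stands, and it rules out two stronger readings. A reader might infer that the SAP hides the preterm signal or gives up the randomised comparison; the retained tables show otherwise. A reader might also infer that 4.6.2 directs a null preterm column to be taken as evidence of safety; it states no rule for interpreting a null or reversed stratum. What the reply does not remove is the stated purpose. A descriptive label does not make a post-dosing stratum suitable for judging consistency of effect.

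On the boundary, the reply is that the same cut stands in Protocol 9.4.6.1, the model is exploratory and its code may be adjusted. That may explain the cut, but SAP 6.1.2.1 already uses 37 or above versus below 37 for that very protocol item.

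The simulation is open to the reply that every rate is assumed, that the larger excesses need healthier extra preterm infants, and that twins are eligible but not modelled. These points are fair, which is why a range is given.

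**Conclusion.** The point holds as a fault of stated purpose and of one category boundary. That the strata are not randomised groups, and that preterm birth is 100% and 0% within them, follows from timing and definition and needs no assumed rate. The size of the misreading risk does: at 252:126 the excess chance of a contradictory preterm column runs from about 2 to 34 points over the settings tried.

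The gagebg1 error affects a covariate in an exploratory model. A reader might infer that preterm safety counts are wrong; they are not, because the safety tables use the correct cut. Nor do the documents show a preterm imbalance in this trial: the signal cited is from RSV MAT-009.

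The replaced mother's-age split is a documentation gap only. Protocol 9.4.1.1 splits infant safety by mother's age, SAP 4.2.1.1 and 4.3.1.1 use GA at birth instead, and SAP 4.8 does not say so. SAP 4.6.1 keeps sub-analyses for 15 to 17 year olds as a partial substitute. At the planned minimum of 18 adolescents, the 2:1 split would be about 12 versus 6.

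**What to change.** 1. **SAP 4.6.2:** take GA at birth off the effect-consistency list. Keep the safety and antibody tables by GA at birth as descriptive, and name the overall by-group table as the treatment comparison.
2. **SAP 4.3.3:** recode gagebg1 to 37 weeks or above versus below 37, and note that Protocol 9.4.6.1 carries the other cut.
3. **SAP 4.2.2.1, 4.3.2.1 and 4.3.3:** report the between-group antibody models at delivery and in infants without gagebg1 and without the dosing-to-delivery interval, alongside any version that includes them. Run the infant model on the Full Analysis Set too, whether or not the 5% exclusion trigger in SAP 4.1 is met. That set does not exclude on the interval, although it still needs a live birth and a sample result.
4. **SAP 4.8 (minor):** declare that GA at birth replaces the mother's-age split of infant safety. Restoring that split is optional.

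The cost is a few sentences of SAP text, one changed boundary and a few extra descriptive model runs. No table is lost and no protocol amendment is needed. The term and preterm tables lose only their status as evidence on consistency of effect.

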5.1. Inclusion criteria

5.1.1. Maternal participants

Maternal participants must satisfy ALL the following criteria at study entry:

- Participants who, in the opinion of the investigator, can and will comply with the requirements of the protocol (e.g. completion of diaries, return for follow-up visits).
- Participants and legally acceptable representatives (LARs) who give written or witnessed/thumb printed informed consent after the study has been explained according to local regulatory requirements, and before any study specific procedures are performed. The informed consent given at screening should (consistent with local regulations / guidelines) either:
 - include consent for both the maternal participant's participation* and participation of the infant after the infant's birth, or
 - include consent for the maternal participant's participation* and expressed willingness to consider permitting the infant to take part after the infant's birth (if local regulations/guidelines require parent(s) to provide an additional informed consent after the infant's birth).

** Written informed consent obtained from parents/LARs and written informed assent obtained from the maternal participant if she is less than legal age, or written informed consent obtained from the participant if the participant has achieved legal age. The legal age is determined according to local regulations in each participating country.*

In case the legal age is achieved during the conduct of the study, an additional written informed consent from the maternal participant should be obtained at the time of the legal age.

- both mother and father should consent if local regulations / guidelines require it.
 - Pre-pregnancy Body Mass Index (BMI) (based on participant's report) 18.5 to 39.9 kg/m², inclusive.
 - Healthy (as established by medical history and clinical examination) adolescent pregnant women, 15 to 17 YOA, inclusive, at the time of study intervention administration.
- OR
- Pregnant women, 18 to 49 YOA, inclusive, at the time of study intervention administration with:

- HIV infection (as confirmed by local standard of care serologic tests)

AND/OR

- Obstetric complications or risk factors during the current pregnancy, where the expectant management of the pregnancy is possible and without evidence of non-reassuring fetal status (only cases for which fetal heart rate can be ascertained) as follows:

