6.3.3. Intervention allocation to the participant (Amended 15 March 2022)

The randomization algorithm will use a stratification procedure accounting for maternal age at the time of study intervention administration (<18, ≥18 YOA) and a minimization procedure accounting for (a) gestational age at the time of study intervention administration (<28^{0/7}; ≥28^{0/7} weeks), (b) pre-existing HIV infection and obstetric complication status (HIV present and obstetric complication present, HIV present and obstetric complication absent, or HIV absent and obstetric complication present) for participants ≥18 YOA only, and (c) center. Minimization factors will have equal weight in the minimization algorithm.

Once a participant identification number is allocated, the randomization system will determine study group and will provide the study intervention number to be used for the dose.

When an automated, internet-based system (SBIR) is not available, please refer to the SBIR user guide or SPM for specific instructions.

Refer to the SPM for additional information about the study intervention number allocation.

Note: Due to the recent safety signal, there will be no further enrollment and vaccination of maternal participants

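### By design, each of the SAP's two adult splits (HIV; obstetric complications) carries the other factor with it, so a difference in vaccine effect across either split cannot be attributed to the factor it names

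*SAP*

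**What the plan says.** Protocol 5.1.1 sets the adult entry condition: "Pregnant women, 18 to 49 YOA, inclusive, at the time of study intervention administration with" either "HIV infection (as confirmed by local standard of care serologic tests") or "Obstetric complications or risk factors during the current pregnancy, where the expectant management of the pregnancy is possible", the two limbs being joined by and/or. Uncomplicated twin gestation is listed under the second limb. Adolescents enter separately, as healthy.

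Protocol 6.3.3 carries this structure into the allocation. For adults, the minimisation factor has exactly three levels: "HIV present and obstetric complication present, HIV present and obstetric complication absent, or HIV absent and obstetric complication present". There is no level for neither condition.

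SAP 4.6.2 states the purpose: "Subgroup analyses of the primary endpoints will be made to assess consistency of the intervention effect across the following subgroups". Its list includes "Pre-existing HIV infection status: present vs absent (for maternal participants ≥ 18 YOA only") and "Pre-existing obstetric complications: present vs absent (for maternal participants ≥ 18 YOA only"). It does not list the three-level factor or a cross-classification of the two conditions. It adds a size rule, from which the split by mother's age is exempt: "if the number of participants is too small (less than 10%) within above mentioned subgroup, then the subgroup categories may be redefined prior to final" [...]. The section then spells out tables only for maternal age and for gestational age at birth, and leaves further subgroup analyses to judgement.

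**The concern.** A present/absent split is normally read as varying one factor while the rest of the population stays roughly the same. Here that cannot happen. With no eligible adult in the neither-condition cell, the absent level of each split consists wholly of women who have the other condition.

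The section is meant to show whether the vaccine effect is consistent. If the effect differs between complications present and absent, the table cannot say whether complications or HIV lie behind it, and the same holds for the HIV split. Two real modifications can also offset each other and look like consistency. The primary maternal endpoints include pathways to preterm birth, the obstetric limb includes threatened preterm labour and twins, and enrolment stopped over a preterm-birth and neonatal-death signal in a related trial (Protocol 2.3). These tables could therefore attract attention.

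**Working it through.** No sample-size or power figure is involved. The point is structural, so the check is to list the cells and then see what each split estimates.

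**Cells** (entry from Protocol 5.1.1, levels from Protocol 6.3.3, splits from SAP 4.6.2):

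| HIV | Complication or risk factor | Eligible adult | Minimisation level | HIV split | Complication split |
|---|---|---|---|---|---|
| yes | yes | yes | HIV plus complication | present | present |
| yes | no | yes | HIV only | present | absent |
| no | yes | yes | complication only | absent | present |
| no | no | no | none | - | - |

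Complications absent is a single cell, HIV only, so it is 100% HIV-positive. HIV absent is a single cell, complication only, so it is 100% complicated. Neither result needs any assumption about recruitment.

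**What each split estimates.** Let p11, p10 and p01 be the shares of adults with both conditions, HIV only and complication only. Suppose HIV changes the vaccine effect by a and a complication changes it by b, additively, and that a subgroup's effect is the share-weighted average. Then:

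- HIV split = a + b·p11/(p11+p10) - b = a - b·p10/(p11+p10)
- Complication split = b + a·p11/(p11+p01) - a = b - a·p01/(p11+p01)

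The documents do not give the shares. Assume 10%, 20% and 70%. Of the 378 - 18 = 360 adults at most that were planned, that is 36, 72 and 252. The weights are 0.20/0.30 = 0.667 and 0.70/0.80 = 0.875.

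| True a (HIV) | True b (complication) | HIV split shows | Complication split shows |
|---|---|---|---|
| 1 | 0 | 1.000 | -0.875 |
| 0 | 1 | -0.667 | 1.000 |
| 1 | 1 | 0.333 | 0.125 |

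With assumed shares of 5%, 10% and 85%, the two spurious values are -0.944 and -0.667, and the last row becomes 0.333 and 0.056. If no woman has both conditions, the splits give a - b and b - a: one partition with the labels swapped.

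**HIV imbalance across the complication split.** If h is the share of adults with HIV and c the share of those who also have a complication, HIV prevalence in the complications-present group is hc/((1-h)+hc).

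| h | c | HIV prevalence, complications present | HIV-plus-complication share (hc) |
|---|---|---|---|
| 0.10 | 0.10 | 0.01/0.91 = 1.1% | 1% |
| 0.20 | 0.30 | 0.06/0.86 = 7.0% | 6% |
| 0.40 | 0.50 | 0.20/0.80 = 25.0% | 20% |

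Against 100% in the absent group, the gap is about 75 to 99 percentage points over this assumed range. In two of the three cases the HIV-plus-complication group is under 10% of adults.

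**Does the plan separate the factors elsewhere?** SAP 4.3.3 names HIV status as a covariate that could be added to an exploratory immunogenicity model. Complication status is not named, and the subgroup section plans no model for the safety endpoints. The under-10% rule is triggered by size, not by overlap.

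**The case against.** The strongest reply accepts the structure and disputes the consequence. Most of it stands.

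- **Within-subgroup comparisons are sound.** Arms are randomised and minimised on this same three-level factor. A reader might infer that the subgroup estimates themselves are biased; the documents do not support that.
- **Prognosis is not the problem.** A reader might infer that an effect of HIV on antibody levels, or of complications on preterm birth, would show up as an effect of the other factor. It would affect both arms of a subgroup alike, so on the scale where the vaccine effect is constant it does not mimic modification. Only modification of the vaccine effect by the other factor misleads, and the documents give no evidence that it occurs.
- **The plan does not fail altogether.** It can show whether the effect looks similar across the listed groups. It cannot assign a difference to one factor, and SAP 4.6.2 does not say that it will.
- **Commitment is loose.** Protocol 9.4.1 makes subgroup analyses optional, and SAP 4.6.2 details only the age and gestational-age tables. All analyses are descriptive.
- **Part of the remedy is implicit.** If both splits are run, two of the three columns already exist under other labels, and event counts for the third follow by subtraction (HIV present minus complications absent).
- **The remedy can undo itself.** Merging a small HIV-plus-complication group into a neighbour under the 10% rule recreates one of the binary splits.

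What remains is that both splits are listed for assessing consistency of effect, under labels that suggest a separation the population does not allow. The last point has to be built into the fix.

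**Conclusion.** The point holds as one of attribution and labelling. Each absent subgroup consists entirely of women with the other condition, so a difference in vaccine effect across either split cannot be assigned to the named factor, and similarity across a split does not rule out modification by either.

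Two assumptions carry this. First, the SAP's term obstetric complications is taken to cover the protocol's complications or risk factors. The three-level factor implies it, but the SAP does not say so; on a narrower reading, an HIV-negative adult with twins alone would fall in a fourth cell that minimisation does not have. Second, the 100% figures apply to eligible adults, so an adult enrolled in violation of the entry criteria could have neither condition.

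The size of any misattribution is not known. The 75 to 99 point gap and the -0.875 and -0.667 values depend on assumed shares and on additive modification. Because the analyses are descriptive, the two splits are loosely committed and enrolment has stopped, this is a low-cost improvement in interpretability and not a threat to the trial's conclusions.

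**What to change.** In SAP 4.6.2:

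1. Replace the two binary splits with the three minimisation levels: HIV only; HIV plus complication; complication only.
2. State that complication covers all the protocol's obstetric complications or risk factors, including uncomplicated twin gestation.
3. If single-factor contrasts are wanted, compare HIV with no HIV among women with a complication, and complication with no complication among women with HIV. Both rest on the HIV-plus-complication group, and neither is a randomised comparison between groups.
4. Exempt this factor from merging under the 10% rule. If the HIV-plus-complication group is below 10%, show it descriptively and state that the two factors cannot be separated.

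If the binary tables are kept, the minimum is a cross-tabulation of HIV by complication in each arm and a footnote saying that neither split isolates its factor.

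The cost is SAP wording and one three-column table in place of two two-column tables. The factor is already held in the randomisation system, so no new data are needed.
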